## **7.2.3 Immediate Reporting of Adverse Events**

### **7.2.3.1 Serious Adverse Events**

A serious adverse event is any adverse event occurring at any dose or during any use of MSD's product that:

- Results in death;
- Is life threatening;
- Results in persistent or significant disability/incapacity;
- Results in or prolongs an existing inpatient hospitalization;
- Is a congenital anomaly/birth defect;
- Is an other important medical event.

**Note:** In addition to the above criteria, adverse events meeting either of the below criteria, although not serious per ICH definition, are reportable to MSD in the same timeframe as SAEs to meet certain local requirements. Therefore, these events are considered serious by MSD for collection purposes.

- Is a new cancer (that is not a condition of the study);

- Is associated with an overdose.

Refer to [Table 10](#) for additional details regarding each of the above criteria.

For the time period beginning when the consent form is signed until treatment allocation/randomization, any serious adverse event, or follow up to a serious adverse event, including death due to any cause, other than progression of the cancer under study (reference Section 7.2.3.3 for additional details) that occurs to any subject must be reported within 24 hours to MSD if it causes the subject to be excluded from the trial, or is the result of a protocol-specified intervention, including but not limited to washout or discontinuation of usual therapy, diet, placebo treatment or a procedure.

For the time period beginning at treatment allocation/randomization through 90 days following cessation of treatment, or 30 days following cessation of trial treatment if the subject initiates new anticancer therapy, whichever is earlier, any serious adverse event, or follow up to a serious adverse event, including death due to any cause other than progression of the cancer under study (reference Section 7.2.3.3 for additional details) whether or not related to MSD's product, must be reported within 24 hours to MSD either by electronic media or paper. Electronic reporting procedures can be found in the EDC data entry guidelines. Paper reporting procedures can be found in the Investigator Trial File Binder (or equivalent).

Additionally, any serious adverse event, considered by an investigator who is a qualified physician to be related to MSD's product that is brought to the attention of the investigator at any time following consent through the end of the specified safety follow-up period specified in the paragraph above, or at any time outside of the time period specified in the previous paragraph also must be reported immediately to MSD.

All subjects with serious adverse events must be followed up for outcome.

### **7.2.3.2 Events of Clinical Interest**

Selected non-serious and serious adverse events are also known as Events of Clinical Interest (ECI) and must be reported to MSD.

For the time period beginning when the consent form is signed until treatment allocation/randomization, any ECI, or follow up to an ECI, that occurs to any subject must be reported within 24 hours to MSD if it causes the subject to be excluded from the trial, or is the result of a protocol-specified intervention, including but not limited to washout or discontinuation of usual therapy, diet, placebo treatment or a procedure.

For the time period beginning at treatment allocation/randomization through 30 days following cessation of treatment, any ECI, or follow up to an ECI, whether or not related to MSD's product, must be reported within 24 hours to MSD, either by electronic media or paper. Electronic reporting procedures can be found in the EDC data entry guidelines. Paper reporting procedures can be found in the Investigator Trial File Binder (or equivalent).

Events of clinical interest for this trial include:

1. an overdose of MSD's product, as defined in Section 7.2.1 - Definition of an Overdose for This Protocol and Reporting of Overdose to MSD, that is not associated with clinical symptoms or abnormal laboratory results.
2. an elevated AST or ALT lab value that is greater than or equal to 3X the upper limit of normal and an elevated total bilirubin lab value that is greater than or equal to 2X the upper limit of normal and, at the same time, an alkaline phosphatase lab value that is less than 2X the upper limit of normal, as determined by way of protocol-specified laboratory testing or unscheduled laboratory testing.\*

\*Note: These criteria are based upon available regulatory guidance documents. The purpose of the criteria is to specify a threshold of abnormal hepatic tests that may require an additional evaluation for an underlying etiology. The trial site guidance for assessment and follow up of these criteria can be found in the Investigator Trial File Binder (or equivalent).

### **7.2.3.3 Protocol-Specific Exceptions to Serious Adverse Event Reporting**

Efficacy endpoints as outlined in this section will not be reported to MSD as described in Section 7.2.3. - Immediate Reporting of Adverse Events to MSD.

Specifically, the suspected/actual events covered in this exception include any event that is disease progression of the cancer under study.

Unblinded aggregated efficacy endpoint events and safety data will be monitored to ensure the safety of the subjects in the trial. Any suspected endpoint which upon review is not progression of the cancer under study will be forwarded to global safety as a SAE within 24 hours of determination that the event is not progression of the cancer under study

### **7.2.4 Evaluating Adverse Events**

An investigator who is a qualified physician will evaluate all adverse events according to the NCI Common Terminology for Adverse Events (CTCAE), version v4.0. Any adverse event which changes CTCAE grade over the course of a given episode will have each change of grade recorded on the adverse event case report forms/worksheets.

All adverse events regardless of CTCAE grade must also be evaluated for seriousness.

Table 10 Evaluating Adverse Events

An investigator who is a qualified physician, will evaluate all adverse events as to:

V4.0 CTCAE Grading	Grade 1	Mild; asymptomatic or mild symptoms; clinical or diagnostic observations only; intervention not indicated.
	Grade 2	Moderate; minimal, local or noninvasive intervention indicated; limiting age-appropriate instrumental ADL.
	Grade 3	Severe or medically significant but not immediately life-threatening; hospitalization or prolongation of hospitalization indicated; disabling; limiting self-care ADL.
	Grade 4	Life threatening consequences; urgent intervention indicated.
	Grade 5	Death related to AE
Seriousness	A serious adverse event is any adverse event occurring at any dose or during any use of MSD's product that:	
	† Results in death ; or	
	† Is life threatening ; or places the subject, in the view of the investigator, at immediate risk of death from the event as it occurred (Note: This does not include an adverse event that, had it occurred in a more severe form, might have caused death.); or	
	† Results in a persistent or significant disability/incapacity (substantial disruption of one's ability to conduct normal life functions); or	
	† Results in or prolongs an existing inpatient hospitalization (hospitalization is defined as an inpatient admission, regardless of length of stay, even if the hospitalization is a precautionary measure for continued observation. (Note: Hospitalization for an elective procedure to treat a pre-existing condition that has not worsened is not a serious adverse event. A pre-existing condition is a clinical condition that is diagnosed prior to the use of a Merck product and is documented in the patient's medical history.); or	
	† Is a congenital anomaly/birth defect (in offspring of subject taking the product regardless of time to diagnosis); or	
	Is a new cancer (that is not a condition of the study) (although not serious per ICH definition, is reportable to MSD within 24 hours to meet certain local requirements); or	
	Is an overdose (whether accidental or intentional). Any adverse event associated with an overdose is considered a serious adverse event for collection purposes. An overdose that is not associated with an adverse event is considered a non-serious event of clinical interest and must be reported within 24 hours.	
	Other important medical events that may not result in death, not be life threatening, or not require hospitalization may be considered a serious adverse event when, based upon appropriate medical judgment, the event may jeopardize the subject and may require medical or surgical intervention to prevent one of the outcomes listed previously (designated above by a †).	
Duration	Record the start and stop dates of the adverse event. If less than 1 day, indicate the appropriate length of time and units	
Action taken	Did the adverse event cause MSD's product to be discontinued?	
Relationship to MSD's product	Did MSD's product cause the adverse event? The determination of the likelihood that MSD's product caused the adverse event will be provided by an investigator who is a qualified physician. The investigator's signed/dated initials on the source document or worksheet that supports the causality noted on the AE form, ensures that a medically qualified assessment of causality was done. This initialed document must be retained for the required regulatory time frame. The criteria below are intended as reference guidelines to assist the investigator in assessing the likelihood of a relationship between the test drug and the adverse event based upon the available information. The following components are to be used to assess the relationship between MSD's product and the AE ; the greater the correlation with the components and their respective elements (in number and/or intensity), the more likely MSD's product caused the adverse event (AE):	
	Exposure	Is there evidence that the subject was actually exposed to MSD's product such as: reliable history, acceptable compliance assessment (pill count, diary, etc.), expected pharmacologic effect, or measurement of drug/metabolite in bodily specimen?
	Time Course	Did the AE follow in a reasonable temporal sequence from administration of MSD's product? Is the time of onset of the AE compatible with a drug-induced effect (applies to trials with investigational medicinal product)?
	Likely Cause	Is the AE not reasonably explained by another etiology such as underlying disease, other drug(s)/vaccine(s), or other host or environmental factors

The following components are to be used to assess the relationship between the test drug and the AE: (continued)	
Relationship to MSD's product (continued)	
Dechallenge Was MSD's product discontinued or dose/exposure/frequency reduced?                      If yes, did the AE resolve or improve?                      If yes, this is a positive dechallenge. If no, this is a negative dechallenge.                      (Note: This criterion is not applicable if: (1) the AE resulted in death or permanent disability; (2) the AE resolved/improved despite continuation of MSD's product; or (3) the trial is a single-dose drug trial); or (4) MSD's product(s) is/are only used one time.)

	
Rechallenge Was the subject re-exposed to MSD's product in this study?                      If yes, did the AE recur or worsen?                      If yes, this is a positive rechallenge. If no, this is a negative rechallenge.                      (Note: This criterion is not applicable if: (1) the initial AE resulted in death or permanent disability, or (2) the trial is a single-dose drug trial); or (3) MSD's product(s) is/are used only one time).                      NOTE: IF A RECHALLENGE IS PLANNED FOR AN ADVERSE EVENT WHICH WAS SERIOUS AND WHICH MAY HAVE BEEN CAUSED BY MSD'S PRODUCT, OR IF REEXPOSURE TO MSD'S PRODUCT POSES ADDITIONAL POTENTIAL SIGNIFICANT RISK TO THE SUBJECT, THEN THE RECHALLENGE MUST BE APPROVED IN ADVANCE BY THE MSD CLINICAL DIRECTOR AS PER DOSE MODIFICATION GUIDELINES IN THE PROTOCOL.

	
Consistency with Trial Treatment Profile Is the clinical/pathological presentation of the AE consistent with previous knowledge regarding MSD's product or drug class pharmacology or toxicology?

The assessment of relationship will be reported on the case report forms /worksheets by an investigator who is a qualified physician according to his/her best clinical judgment, including consideration of the above elements.	
Record one of the following	Use the following scale of criteria as guidance (not all criteria must be present to be indicative of a MSD's product relationship).
Yes, there is a reasonable possibility of MSD's product relationship.	There is evidence of exposure to MSD's product. The temporal sequence of the AE onset relative to the administration of MSD's product is reasonable. The AE is more likely explained by MSD's product than by another cause.
No, there is not a reasonable possibility of MSD's product relationship	Subject did not receive MSD's product OR temporal sequence of the AE onset relative to administration of MSD's product is not reasonable OR the AE is more likely explained by another cause than MSD's product. (Also entered for a subject with overdose without an associated AE.)

## **7.2.5 Responsibility for Reporting Adverse Events**

All Adverse Events will be reported to regulatory authorities, IRB/IECs and investigators in accordance with all applicable global laws and regulations, i.e., per ICH Topic E6 (R1) Guidelines for Good Clinical Practice.

## **7.3 TRIAL GOVERNANCE AND OVERSIGHT**

### **7.3.1 Scientific Advisory Committee**

The Scientific Advisory Committee (SAC) comprises both Sponsor and non-Sponsor scientific experts who provide input with respect to trial design, interpretation of trial results and subsequent peer-reviewed scientific publications.

### **7.3.2 Executive Oversight Committee**

The Executive Oversight Committee (EOC) comprises members of Sponsor and MSD Senior Management. The EOC will receive and decide upon any recommendations made by the Data Monitoring Committee (DMC) regarding the trial.

### **7.3.3 Data Monitoring Committee**

To supplement the routine trial monitoring outlined in this protocol, an external Data Monitoring Committee (DMC) will monitor the interim data from this trial. The voting members of the committee are external to the Sponsor. The members of the DMC must not be involved with the trial in any other way (e.g., they cannot be trial investigators) and must have no competing interests that could affect their roles with respect to the trial.

The DMC will make recommendations to the EOC regarding steps to ensure both subject safety and the continued ethical integrity of the trial. Also, the DMC will review interim trial results, consider the overall risk and benefit to trial participants (see Section 8.7 - Interim Analyses) and recommend to the EOC if the trial should continue in accordance with the protocol.

Specific details regarding composition, responsibilities, and governance, including the roles and responsibilities of the various members and the protocol team; meeting facilitation; the trial governance structure; and requirements for and proper documentation of DMC reports, minutes, and recommendations will be described in a separate charter that is reviewed and approved by the DMC. The DMC will monitor the trial at an appropriate frequency, as described in the detailed DMC charter.

A DMC recommendation will be communicated to as agreed to in the DMC charter.

## 8.0 STATISTICAL ANALYSIS PLAN

This section outlines the statistical analysis strategy and procedures for the study. If, after the study has begun, but prior to any unblinding/final database lock, changes are made to primary and/or key secondary hypotheses, or the statistical methods related to those hypotheses, then the protocol will be amended (consistent with ICH Guideline E-9).

### 8.1 Statistical Analysis Plan Summary

Key elements of the statistical analysis plan are summarized below; the comprehensive plan is provided in Sections 8.2-8.12.

Study Design Overview	A Phase 3 Randomized, Double-Blind, Placebo-Controlled Study of Pembrolizumab in Combination With Epacadostat or Placebo in Subjects with Unresectable or Metastatic Melanoma
Treatment Assignment	Following stratification by PD-L1 expression (Positive; Negative/indeterminate) and BRAF mutation status (BRAF mutant and received prior BRAF directed treatment; BRAF mutant no prior BRAF directed treatment; BRAF wild type) patients will be randomized 1:1 to treatment with pembrolizumab in combination with either epacadostat or placebo
Analysis Populations	Efficacy: Intent to Treat (ITT) Safety: All Subjects as Treated (ASaT)
Primary Endpoint(s)	1. Progression-free survival (PFS) 2. Overall survival (OS)
Key Secondary Endpoints	1. Objective response rate (ORR)
Statistical Methods for Key Efficacy/Immunogenicity/ Pharmacokinetic Analyses	The primary hypotheses will be evaluated by comparing treatment with pembrolizumab and epacadostat to treatment with pembrolizumab and placebo on (1) PFS and (2) OS using a stratified log-rank test. Estimation of the hazard ratio will be done using a Cox regression model. Event rates over time will be estimated within each treatment group using the Kaplan-Meier method.
Statistical Methods for Key Safety Analyses	The analysis strategy for safety endpoints will depend upon the safety tier (see Section 8.6.2). There are no Tier 1 safety endpoints. Descriptive statistics will be provided for the rate of Tier 2 safety endpoints, as well as 95% confidence intervals for the treatment comparisons.


Interim Analyses
	
Two interim analyses will be performed in this study. Results will be reviewed by an external data monitoring committee. These interim analyses are summarized below. Details are provided in Section 8.7. An analysis of ORR may be conducted using data from interim analysis 2 (IA2).
 
 
• IA 1: 
 
○ Timing: To be performed when approximately 331 PFS events are observed. This analysis is expected to be performed about 12 months after enrollment starts. Approximately 100 OS events are expected at IA1.
 
○ Testing: Inferential analyses for PFS and OS will be performed.
 
 
 
• IA 2: 
 
○ Timing: to be performed when approximately 420 PFS events are observed. This is the final PFS analysis and is expected to be performed about 24 months after enrollment starts. Approximately 200 OS events are expected at IA2.
 
○ Testing: Inferential analyses for PFS and OS will be performed.
 
 
 
• Final analysis 
 
○ Timing: To be performed when approximately 293 OS events are observed. This is the final OS analysis and is expected to be performed about 45 months after enrollment starts.
 
○ Testing: Inferential analyses for OS will be performed.
 
 
 

Multiplicity
	
The Type-I error rate over the multiple endpoints tested, as well as for the multiple analyses planned, will be controlled by sequential interim monitoring and the methods of Maurer and Bretz [59]


Sample Size and Power
	
The planned sample size was initially approximately 600 subjects. Japan will begin enrolling late in the enrollment period, and must meet a minimum enrollment regulatory requirement. Therefore enrollment from Japan may continue after enrollment in other countries ends. Total enrollment is now expected to be approximately 700 subjects. For PFS, the trial has ~98% power to demonstrate that pembrolizumab and epacadostat is superior to pembrolizumab and placebo at an overall 1-sided 1.25% alpha-level. For OS, the trial has ~79% power to demonstrate that pembrolizumab and epacadostat is superior to pembrolizumab and placebo at an initial overall 1-sided 1.25% alpha-level. Should the PFS comparison be statistically significant, the 1.25% alpha will be re-assigned to OS. Should the OS comparison be statistically significant, the 2.5% alpha will be re-assigned to ORR. Should the total alpha assigned to OS be 2.5%, the power to demonstrate improved OS with the combination will be about 86%. The treatment effect (true hazard rate) is assumed to be 0.65 for PFS and 0.70 for OS.

Based on review of IA2 data, the DMC recommended that all subjects stop oral therapy (epacadostat/placebo). After study completion, only selected analyses will be performed.

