#### 7.1.8.4.3 Survival Follow-Up

**NOTE: As of Amendment 10, this section is no longer applicable. Subjects currently in survival follow-up are considered to have completed the study; these subjects will no longer be contacted for survival information. Assessment and recording of AEs will be performed as per Section 7.2.**

Subjects who experience disease progression by site assessment or start a new anti-cancer therapy will move into the Survival Follow-Up Phase and should be contacted by telephone approximately every 9 weeks to assess for survival status until death, withdrawal of consent, or the end of the study, whichever occurs first.

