## **8.8 Multiplicity**

The multiplicity strategy specified in this section will be applied to the overall ITT population for the testing of primary hypotheses. The overall type I error is strongly controlled at 2.5% (one-sided) for the multiple endpoints tested, as well as for the multiple analyses of overall survival planned using the methods of Maurer and Bretz [59], with 1.25% allocated up front to the PFS hypothesis and 1.25% allocated up front to the OS hypotheses. The trial is considered statistically positive if either PFS or OS is positive.

The superiority of PFS will be tested at 1.25% in this study. If the pembrolizumab + epacadostat combination regimen demonstrates superior PFS, the 0.0125 alpha will be re-assigned to the comparison of OS. Should the OS comparison be statistically significant, the alpha assigned to OS will be reassigned to the comparison of ORR.

A graphical display of the plans for re-allocation of alpha is displayed in [Figure 3](#).

[figure not shown]

Figure 3 Graphical Display of Testing Strategy

For the PFS and OS hypothesis, an exponential alpha-spending function (see Anderson and Clark [60]) with  $\nu=0.75$  (approximating an O'Brien-Fleming boundary) will be used. For PFS the cumulative alpha will be 1.25% unless OS and ORR are statistically significant, in which case the 1.25% alpha associated with OS will be reallocated to PFS and testing will be done at 2.5% alpha. For OS, the cumulative alpha will be 1.25% (if PFS superiority is not demonstrated) or 2.5% (if PFS superiority is demonstrated).

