**ORR analysis:** Should the definitive OS analysis be statistically significant, the definitive ORR analysis will be performed using the data available at IA2. Assuming the available alpha for the ORR comparison is 2.5% and an ORR of 35% for the pembrolizumab + placebo regimen, the study has ~97% power to detect an ORR rate for the combination regimen of 50%.

The above calculations are based on the following assumptions (in addition to the interim analysis plan in Section 8.7): 1) OS for the pembrolizumab + placebo regimen follows a distribution with a “cure” rate of 35%, with survival for the remaining 65% of patients following an exponential distribution with a median of 14 months; 2) PFS follows a distribution with a “cure” rate of 30%, with PFS for the remaining 70% of patients following an exponential distribution with a median of 4.75 months in the pembrolizumab + placebo regimen; 3) the hazard ratio for OS between the pembrolizumab + epacadostat combination and pembrolizumab + placebo is 0.7; 4) hazard ratio for PFS between the pembrolizumab + epacadostat combination and pembrolizumab + placebo is 0.65 and 5) an enrollment period of approximately 12 months. The sample size and power calculation were performed in the software R package gsDesign (see R code, Section 12.10).

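### Does the Section 8.1 summary give ORR 2.5% alpha after an OS win even when PFS has failed?

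*Combined protocol and SAP*

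**What the plan says.** The sample size and power row of the Section 8.1 table first sends the 1.25% held by PFS to OS if PFS is significant. It then says "Should the OS comparison be statistically significant, the 2.5% alpha will be re-assigned to ORR". The sentence after that gives OS power for one case: "Should the total alpha assigned to OS be 2.5" per cent.

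Section 8.8 sets out the multiplicity rule. The alpha is split 1.25% to PFS and 1.25% to OS. On the step to ORR it says "Should the OS comparison be statistically significant, the alpha assigned to OS will be reassigned to the comparison of ORR". On what OS holds it says "For OS, the cumulative alpha will be 1.25% (if PFS superiority is not demonstrated) or 2.5% (if PFS superiority is demonstrated"). The claim for the whole procedure is "The overall type I error is strongly controlled at 2.5% (one-sided) for the multiple endpoints tested". Section 8.8 also sends 1.25% from OS back to PFS if OS and ORR both succeed.

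Section 8.9.1 gives ORR power of about 97% for 35% against 50%, introduced by "Assuming the available alpha for the ORR comparison is 2.5" per cent. Section 8.1 describes itself as key elements only and says "the comprehensive plan is provided in Sections 8.2-8.12".

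**The concern.** An OS-only win is a real branch of this design, because Sections 3.1 and 8.8 call the trial positive if either primary endpoint succeeds. In that branch the Section 8.1 sentence, taken alone, puts the ORR threshold at 0.025, while Section 8.8 puts it at 0.0125. An ORR p-value between the two would be a success under one and a failure under the other.

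The looser threshold would also spend alpha that OS does not hold. PFS would already have used its 1.25% and ORR would get 2.5%, so the bound on familywise error becomes 1.25% + 2.5% = 3.75%. That would contradict the strong control at 2.5% claimed in Section 8.8.

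**Working it through.** **1. Inputs.** Initial one-sided alpha is 1.25% each for PFS and OS (Section 8.8). PFS looks are at 331 and 420 events and OS looks at 100, 200 and 293 (Table 15). The hazard ratios are 0.65 and 0.70, and ORR is 35% against 50% (Section 8.9.1). Spending is exponential with ν = 0.75 (Section 8.8). Enrolment was planned at about 600 and is now expected to be about 700, randomised 1:1. The documents give no correlation between the PFS and ORR tests, so a range is assumed.

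**2. Reproducing the plan's figures.** Cumulative spend at information fraction t is α^(t^−0.75). For PFS at IA1, t = 331/420 = 0.788, and the spend is 0.0125^1.1955 = 0.0053. The nominal level at IA2 is then 0.0108. The OS levels are 0.00005, 0.0029 and 0.0115. All agree with Table 15. Power is 98.4% for PFS, 78.6% for OS at 1.25% and 85.7% for OS at 2.5%, against about 98%, 79% and 86% stated.

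For ORR with n per arm, power = Φ{[0.15 − z·√(2·0.425·0.575/n)] / √[(0.35·0.65 + 0.50·0.50)/n]}.

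| Alpha | n = 300 | n = 350 |
|---|---|---|
| 2.5% (z = 1.960) | Φ(1.777) = 96.2% | Φ(2.078) = 98.1% |
| 1.25% (z = 2.241) | Φ(1.492) = 93.2% | Φ(1.793) = 96.4% |

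The stated 97% or so lies between the two values at 2.5%.

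**3. Familywise error under each reading.** Take PFS and ORR both null and OS truly effective. With OS certain to win, the error is one minus the probability of no rejection at PFS IA1, PFS IA2 or ORR (tested on IA2 data), where the two PFS looks have correlation √(331/420). At 78.6% OS power, with OS independent of the other two, it is 0.0125 + 0.786 × (that value − 0.0125).

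| Assumed PFS–ORR correlation | 8.1 sentence alone, OS certain | 8.1 sentence alone, OS power 78.6% | 8.8 rule, OS certain | 8.8 rule, OS power 78.6% |
|---|---|---|---|---|
| 0 | 3.7% | 3.2% | 2.5% | 2.2% |
| 0.5 | 3.5% | 3.0% | 2.3% | 2.1% |
| 0.7 | 3.2% | 2.8% | 2.2% | 2.0% |
| 0.9 | 2.8% | 2.5% | 1.8% | 1.7% |

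The excess appears only in the columns where Section 8.8 is set aside.

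**4. How often the difference could matter at the design stage.** PFS fails with probability 1 − 0.984 = 1.6%. If OS is independent, OS wins while PFS fails with probability 1.6% × 78.6% = 1.3%. Within that branch, at the planned 15-point ORR difference, the ORR p-value falls between 0.0125 and 0.025 with probability 96.2% − 93.2% = 3.0% (300 per arm) or about 1.8% (350 per arm). If ORR is null it is 1.25%.

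**5. Reading the passages together.** The three sentences in Section 8.1 form a sequence: PFS wins and OS gains 1.25%; OS wins and 2.5% moves to ORR; OS power if OS holds 2.5%. OS reaches 2.5% only as 1.25% + 1.25% after a PFS win, so without that win there is no 2.5% to pass on. The return step in Section 8.8 fits this: 1.25% going back to PFS after OS and ORR succeed makes sense only if 1.25% passed through ORR while PFS had not yet succeeded. Section 8.9.1 likewise gives 2.5% for ORR as an assumption.

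**The case for a change.** The best case for a change is that each sentence in the Section 8.1 sequence carries its own condition, and the ORR sentence names OS alone. A reader should not have to infer a threshold from neighbouring sentences. Section 8.9.1 does not supply the missing condition, since it quotes ORR power at 2.5% only. The branch is not remote on the trial's own history either: the rationale in the Summary of Changes records that PFS missed its criterion at IA2, the final PFS analysis, so any formal ORR test would have fallen in the OS-only branch. The 1.3% design-stage probability does not describe that situation.

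Most of this stands as a comment on wording. The sentence alone does omit the condition, and naming the alpha held by OS would have been cleaner. What does not stand is the step to a multiplicity defect. Reaching 0.025 for ORR after a PFS failure means following one line of a self-described summary against an explicit rule in the section that governs multiplicity. The same trial history also removes the consequence. ORR testing needs an OS win, the Summary of Changes says OS was unlikely to reach significance, Section 8.1 says only selected analyses will follow, and Section 7.1.8.4.3 says of subjects in survival follow-up that "these subjects will no longer be contacted for survival information". Quoting ORR power at 1.25% (93% to 96%) would add detail but correct nothing, because the existing figure states its alpha.

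**Conclusion.** The concern does not call for a change. The Section 8.1 sentence is a clerical looseness in a summary; Section 8.8 states the rule correctly and completely: ORR receives 1.25% after an OS-only win and 2.5% if PFS has also won. Under that rule, in the scenario examined, familywise error is 1.7% to 2.5% for assumed PFS–ORR correlations from 0 to 0.9. The 2.8% to 3.7% figures need three things together: Section 8.8 ignored, a true OS benefit with none on PFS or ORR, and OS certain to win. At the planned OS power the range is 2.5% to 3.2%.

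This rests on Section 8.8 governing over the summary, as Section 8.1 itself indicates, and on the assumed correlations, which affect the size of the hypothetical excess but not the conclusion. Figure 3, the graph of the alpha transfers, is not reproduced in the text available and was not relied on. Rewording the line would leave every boundary, power, event target and result as it is.
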